7.6 UNANTICIPATED (SERIOUS) ADVERSE DEVICE EFFECT (UADE)

A UADE is any serious adverse effect on health or safety or any life-threatening problem or death caused by, or associated with, a device, if that effect, problem, or death was not previously identified in nature, severity, or degree of incidence in the investigational plan or application (including a supplementary plan or application), or any other unanticipated serious problem associated with a device that relates to the rights, safety, or welfare of subjects.

A UADE is a type of SAE that requires reporting to the Sponsor in accordance with Section 7.9.

7.7 DEVICE DEFICIENCY

A device deficiency is an inadequacy of a medical device with respect to its identity, quality, durability, reliability, safety or performance.

Note: Device deficiencies include malfunctions, use errors and inadequate labelling.

7.8 SAFETY AND TOXICITY MANAGEMENT

The Medical Monitor is responsible for the overall safety monitoring of the clinical trial.

Safety monitoring assessments include but are not limited to:

INO-4800	COVID19-311
Inovio Pharmaceuticals, Inc.	Clinical Protocol

- Incidence of all AEs classified by system organ class, preferred term, severity and causal relationship to clinical trial treatment;
- Changes in laboratory parameters;
- Local and systemic injection site review; special attention will be paid to the examination of the injection site.

7.8.1 ADVERSE EVENT OF SPECIAL INTEREST (AESI)

An adverse event of special interest (serious or non-serious) is one of scientific and medical concern specific to the Sponsor's product or program, for which ongoing monitoring and rapid communication by the Investigator to the Sponsor can be appropriate.

For the purpose of this clinical trial, the AESIs listed in Appendix A are to be reported to the Sponsor in accordance with Section 7.9.

7.8.2 MEDICALLY ATTENDED ADVERSE EVENT (MAAE)

A medically attended adverse event (serious or non-serious) is defined as an adverse event that leads to an unplanned contact with a health care provider.

7.8.3 ABNORMAL LABORATORY VALUE

The Investigator will annotate each abnormal lab value as clinically significant (CS) or not clinically significant (NCS).

Laboratory values that are NCS in the Investigator's opinion should not be reported as an adverse event.

Any abnormal laboratory value that is new in onset or worsened in severity or frequency from the baseline condition and meets one of the following criteria will be recorded as an AE:

- Requires therapeutic intervention or diagnostic tests;
- Leads to discontinuation of further administration of the investigational product in the clinical trial;
- Has accompanying or inducing symptoms or signs;
- Is judged by the Investigator as clinically significant (CS).

Abnormal laboratory values that meet the criteria of an AE or SAE should be reported in accordance with Section 7.9.

7.8.4 CLINICAL TRIAL STOPPING RULES

The Investigator is to immediately notify the Medical Monitor if the following are observed:

- Any SAE related to study treatment (i.e., IP and/or the study device);
- Any Grade 4 AEs related to study treatment (i.e., IP and/or the study device);
- Any report of anaphylaxis related to study treatment (i.e., IP and/or the study device);
- Any suspected Severe COVID-19 disease case (per Sections 3.7.1.1 and Section 3.7.1.2).

INO-4800	COVID19-311
Inovio Pharmaceuticals, Inc.	Clinical Protocol

The Medical Monitor will notify the Chair of the Safety Review Committee (SRC), who will determine whether dosing should be temporarily halted until a more formal review of the case(s) is made. Such a formal review may include an ad hoc meeting of the SRC and/or a consultation with the DSMB Chair. If such a consultation occurs, the DSMB Chair and/or the SRC Chair may decide to convene an ad hoc meeting of the DSMB. Following such a meeting, the DSMB chair will render any recommendations to the SRC Chair. The Sponsor will independently investigate the case(s) and, after review of the DSMB recommendations, will make a final decision regarding continuation of trial dosing. These deliberations will be documented and will be provided to the IRBs and FDA, where required.

In the case of suspected Severe COVID-19 cases, the trial will be paused if a vaccine-toplacebo case split yields a relative risk with a 90% confidence interval lower bound >1. The minimum case split corresponding to this criterion is 8:0. In this scenario, the trial will pause until at least one additional case is accrued and the DSMB can review the data and make a recommendation regarding continued enrollment in the trial.

7.9 SAFETY DATA REPORTING PERIOD, METHOD OF COLLECTION AND SUBMISSION

All AEs will be collected from the time informed consent is obtained through Day 56. MAAEs, AESIs and SAEs only will continue to be collected after the Day 56 visit and will be followed to resolution or stabilization. This information will be captured in the CRF.

If the Investigator determines that the AE meets serious criteria, then the AE will be recorded as an SAE.

SAEs and AESIs will be reported to the Sponsor from the time the subject signs the informed consent until the last visit.

All SAEs (regardless of causal relationship) and AESIs will be reported on the SAE CRF Form and submitted to the Sponsor via EDC within 24 hours of becoming aware of the event. In the event the EDC is unavailable, the SAE/AESI Report Form (paper) should be used and submitted to the Sponsor within 24 hours of becoming aware of the event. In that case, the SAE Report Form will be either emailed to [contact] or faxed to the sponsor within SAE Report Form must be kept at the clinical trial site.

The event will be data entered into the CRF.

[figure not shown]
For the events that are considered an AESI, the Investigator will contact the Sponsor within 24 hours of becoming aware of the event to discuss whether dosing should continue.

Table 11: SAE Contact Information

Sponsor Safety Email: [contact]
Sponsor Safety Fax:
Sponsor Safety Phone:

Table 12: Medical Monitor Direct Contact Information

Primary point of contact, ICON Medical Monitor: , M.D.

All SAEs, treatment-related AEs, MAAEs and AESIs must be followed by the Investigator until resolution or return to baseline status, stabilization of the event (i.e., the expectation that it will remain chronic), even if it extends beyond the clinical trial reporting period or until it is determined that the subject is lost to follow up.

Follow-up information is to be submitted to the Sponsor on an SAE Report Form and within 24 hours of becoming aware of the information.

If medical records are submitted to the Sponsor with the SAE Report Form, the clinical trial site must:

- Redact the medical records of all personal data (e.g., confidential subject data, Personal Identifying Information [PII])
- Provide the subject's assigned identification number (SID) on the records

7.10 Adverse Event Reporting

This section provides details on reporting the safety information.

7.10.1 SUBMITTING THE INITIAL SERIOUS ADVERSE EVENT (SAE) REPORT FORM

The Investigator should include as much safety information as possible when submitting the initial report, but the report must include the following at a minimum:

- The adverse event;
- The subject's assigned identification number (SID);
- Investigational product(s) (IP) and/or study device;
- Investigator causal relationship to the IP(s) and/or study device;
- Serious criteria;
- Reporter name and contact information.

If a case is submitted to the Sponsor with only the "minimum" information, a more detailed or updated follow-up report will be sent to the Sponsor as soon as possible but no later than three (3) calendar days after the date of the initial report.

7.10.2 RECORDING THE EVENT

Investigators should use correct medical terminology/concepts when recording AEs on the EDC and SAE Report Form. The use of colloquialisms and abbreviations should be avoided.

A medical diagnosis, if known, should be recorded rather than individual signs and symptoms. However, if the signs and/or symptoms cannot be medically characterized as a single diagnosis or syndrome, each individual sign and/or symptom should be recorded.

INO-4800	COVID19-311
Inovio Pharmaceuticals, Inc.	Clinical Protocol

If a diagnosis is subsequently established, all previous signs and/or symptoms will be subsumed and replaced with a single medical diagnosis.

7.10.3 Assessing Severity (Intensity)

Severity is used to describe the intensity of a specific event (e.g., mild, moderate, severe).

The Investigator will assess and grade clinical AEs or SAEs (based on discussions with clinical trial subjects) in accordance with CTCAE.

7.10.4 CAUSAL RELATIONSHIP OF CLINICAL MATERIAL TO ADVERSE EVENTS (AES)

A causally related AE is one judged to have a possible, probable or definite relationship to the administration of the IP and/or the study device. An AE may also be assessed as not related to the IP and/or the study device. Because the Investigator is knowledgeable about the subject (e.g., medical history, concomitant medications), administers the IP, and monitors the subject's response to the IP, the Investigator is responsible for reporting AEs and judging the relationship between the administration of the IP and EP and a subsequent AE. The Investigator is aware of the subject's clinical state and may have observed the event, and thus may be sensitive to distinctions between events due to the underlying disease process versus events that may be product-related.

Investigators should use their knowledge of the clinical trial subject, the circumstances surrounding the event, and an evaluation of any potential alternative causes to determine whether an AE is considered to be related to the IP and/or the study device and the causal relationship reported as "Yes" or "No" accordingly. Causality should be assessed by the Investigator as related to drug, related to device, or related to both drug and device (i.e., related to both or indiscernible) by the following criteria:

- Yes there is a reasonable possibility that administration of the clinical trial treatment (drug or device or both drug and device) contributed to the event
- No there is no reasonable possibility that administration of the clinical trial treatment contributed to the event and there are more likely causes

The following guidance should also be taken into consideration:

- Temporal relationship of event to administration of IP and/or EP;
- Course of the event, considering especially the effects of dose reduction, discontinuation of IP, or reintroduction of IP (where applicable);
- Known association of the event with the IP, EP or with similar treatments;
- Known association of the event with the disease under trial;
- Presence of risk factors in the clinical trial subject or use of concomitant medications known to increase the occurrence of the event.

The rationale for the Investigator's causal assessment is to be recorded on the SAE Report Form.

The Sponsor will assess the overall safety of the IP delivered by EP and determine whether to report expeditiously to the regulatory authority(ies).

INO-4800	COVID19-311
Inovio Pharmaceuticals, Inc.	Clinical Protocol

7.11 REPORTING SUSPECTED COVID-19 DISEASE CASES DURING THE TRIAL

For both Phase 2 and Phase 3 segments of the trial, all suspected COVID-19 disease cases based on reported COVID-19 symptoms and/or SARS-CoV-2 test results should be entered into the Suspected COVID-19 Clinical Event CRF within 24 hours of awareness. Cases will be tracked until final determination of whether the case meets criteria of a confirmed COVID-19 disease case, per the case definition. For the Phase 2 segment of the trial, this determination will be made by the Investigator. For the Phase 3 segment, this determination will be made by the EAC.

If the reported COVID-19 disease case is later determined not to be a confirmed COVID-19 case, the event (e.g. symptoms or other diagnosis), if serious, would be reported as an SAE within 24 hours following determination by the Investigator (Phase 2 segment) or notification by EAC (Phase 3 segment).

If the reported COVID-19 disease case is later determined not to be a confirmed COVID-19 case, the event (e.g. symptoms or other diagnosis), if non-serious and if occurring from the time of consent until 28 days post-dose 2, would be reported as an AE following determination by the Investigator (Phase 2 segment) or notification by EAC (Phase 3 segment).

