3.7 EFFICACY ASSESSMENT (PHASE 3 SEGMENT ONLY)

Subjects will receive either active investigational product (INO-4800, dose selected from the Phase 2 segment) or placebo in a 2-dose regimen administered intradermally followed immediately by EP on Days 0 and 28. Subjects will be monitored through regularly scheduled clinic visits and phone calls throughout the trial. Subjects will be regularly tested for SARS-CoV-2 infection using serologic testing. If COVID-19 disease (including severe COVID-19) is suspected based on symptoms or laboratory testing, site personnel will arrange for a clinic visit. Subjects with symptom(s) or a positive SARS-CoV-2 test result will be reviewed by the independent blinded EAC. The EAC will adjudicate all suspected COVID-19 events and determine whether cases meet the case definitions for COVID-19 disease, severe COVID-19 or SARS-CoV-2 asymptomatic infection.

The mechanism for review and confirmation of cases will be outlined in an EAC Charter.

3.7.1 CASE DEFINITION FOR VIROLOGICALLY-CONFIRMED COVID-19 DISEASE:

- Positive testing by SARS-CoV-2 RT-PCR assay (performed at central lab*) with fever (temperature of 100.4°F/38.0°C or higher), or
- Positive testing by SARS-CoV-2 RT-PCR assay (performed at central lab*) with any of the following COVID-19 related symptoms:
 - Feeling feverish or chills
 - Cough
 - Shortness of breath or difficulty breathing
 - Fatigue
 - Muscle or body aches
 - Headache
 - New loss of taste or smell
 - Sore throat
 - Congestion or runny nose
 - Nausea or vomiting
 - Diarrhea

*Local lab results will be accepted if the subject is hospitalized and a sample is not able to be obtained for analysis at central lab.

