7.4 SERIOUS ADVERSE EVENTS (SAEs)

An SAE is any untoward medical occurrence that at any dose:

- Results in death;
- Is life-threatening;
 - Refers to an event in which the subject was at risk of death at the time of the event. It does not refer to an event which hypothetically might have caused death if it were more severe
- Requires inpatient hospitalization or prolongation of existing hospitalization;
 - Includes any hospitalization in which the subject has been admitted to the hospital regardless the length of stay, even if the hospitalization is only a precautionary measure to allow continued observation. However, hospitalization (including hospitalization for an elective procedure) for a pre-existing condition that has not worsened, does not constitute an SAE
- Results in persistent or significant disability/incapacity;
 - A substantial disruption of a person's ability to conduct normal life functions (i.e., the adverse event resulted in a significant, persistent or permanent change, impairment, damage or disruption in the subject's body function/structure, physical activities and/or quality of life)
- Results in congenital anomaly or birth defect and/or;
- An important medical event.

INO-4800	COVID19-311
Inovio Pharmaceuticals, Inc.	Clinical Protocol

 An event that may not be immediately life-threatening or result in death or hospitalization but may jeopardize the subject or may require intervention to prevent one of the other outcomes listed above. Examples of such events are intensive treatment in an emergency room or at home for allergic bronchospasm, blood dyscrasias or convulsions that do not result in hospitalization, or development of drug dependency or drug abuse

Clarification of Serious Adverse Events (SAEs)

- Death itself is not an AE. Death is an outcome of an AE, but when the cause of death has not been provided, use the event term: death of unknown cause;
- Confirmed COVID-19 disease that requires hospitalization is recorded on the Suspected COVID-19 Clinical Event CRF, and not recorded as an SAE;
- COVID-19 disease with an outcome of death is recorded on the Suspected COVID-19 Clinical Event CRF, and not recorded as an SAE;
- The subject may not have been receiving an investigational medicinal product at the occurrence of the event;
- Complications associated with COVID-19 disease that occur or prolong hospitalization are recorded on the Suspected COVID-19 Clinical Event CRF;

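### Sections 7.11 and 7.9 set different SAE clocks for a serious suspected COVID-19 event, leaving a narrow class of events whose SAE report can wait for adjudication

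*Protocol*

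**What the plan says.** All references are to protocol version 7.0 unless noted.

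- **Section 7.9, general rule.** "All SAEs (regardless of causal relationship) and AESIs will be reported on the SAE CRF Form", and these are to be "submitted to the Sponsor via EDC within 24 hours of becoming aware of the event". No exception is made for suspected COVID-19.
- **Section 7.4, exemption.** "Confirmed COVID-19 disease that requires hospitalization is recorded on the Suspected COVID-19 Clinical Event CRF, and not recorded as an SAE". COVID-19 deaths are treated the same way. Section 7.2 likewise removes only confirmed COVID-19 from the definition of an AE.
- **Section 7.11, suspected cases.** Suspicion rests on reported symptoms, test results or both. Such cases "should be entered into the Suspected COVID-19 Clinical Event CRF within 24 hours of awareness". On whether a case is confirmed: "For the Phase 3 segment, this determination will be made by the EAC"; in Phase 2 the Investigator decides. If the answer is no and the event was serious, it "would be reported as an SAE within 24 hours following determination by the Investigator (Phase 2 segment) or notification by EAC (Phase 3 segment".
- **Section 3.7, adjudication.** "The mechanism for review and confirmation of cases will be outlined in an EAC Charter". The protocol gives no turnaround time.
- **Section 7.8.4, notification.** One of the events that must go to the Medical Monitor immediately is "Any SAE related to study treatment (i.e., IP and/or the study device"). The others are related Grade 4 AEs, related anaphylaxis and suspected severe COVID-19.

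**The concern.** The exemption in 7.2 and 7.4 is for confirmed disease. In effect, 7.11 gives the same treatment to suspected disease until someone has ruled on it. In Phase 3 the ruling is not the site's to make, so a site that already holds a negative RT-PCR or another diagnosis does not, on the wording of 7.11, have its SAE clock running.

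The overlap is foreseeable. Tiredness, muscle aches, headache and nausea are solicited vaccine reactions in the diary (Section 6.4), and fatigue, muscle aches, headache and nausea are also qualifying symptoms in the case definition (Section 3.7.1). Soon after a dose, a product reaction and a suspected case can look alike.

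What is at stake is the part of safety reporting tied to SAE status: the SAE report itself, the Investigator's causality rationale, which Section 7.10.4 places on the SAE Report Form, and the related-SAE trigger in 7.8.4.

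**Working it through.** No sample size, power or error rate is involved. The check compares the clocks and then asks which events are left without a prompt route.

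**Step 1. The two deadlines.** Let A be the time the site becomes aware of the serious event and D the time from A until EAC notification (Phase 3) or Investigator determination (Phase 2).

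- Due under 7.9: A + 24 h.
- Due under 7.11: A + D + 24 h.
- Difference: (A + D + 24 h) − (A + 24 h) = D.

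The sections agree only if D is zero. In Phase 3, D is the adjudication time, which the protocol does not bound. In Phase 2, D is the Investigator's own time to a decision. The conflict therefore exists in both segments and is larger in kind in Phase 3, where the site does not control D.

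**Step 2. Does another section supply the exception?** Sections 7.2 and 7.4 do not, because both speak of confirmed disease only. Section 7.9 has no carve-out. No section ranks 7.11 above 7.9 or the reverse.

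**Step 3. Which routes do not depend on D?**

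| Event before adjudication | Route | Timing |
|---|---|---|
| Any suspected COVID-19 case | Suspected COVID-19 Clinical Event CRF (7.11) | 24 h from awareness |
| AESI | SAE form, plus contact with the Sponsor (7.9) | 24 h from awareness |
| Suspected severe COVID-19 | Medical Monitor (7.8.4) | Immediate |
| Related Grade 4 AE | Medical Monitor (7.8.4) | Immediate |
| Related anaphylaxis | Medical Monitor (7.8.4) | Immediate |
| Any other serious event | SAE form; Medical Monitor if related | 24 h from awareness (7.9) or after D (7.11) |

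Only the last row is exposed. An example is a subject admitted to hospital with fever and fatigue, without any severe-COVID-19 criterion of Section 3.7.1.1, without an AESI diagnosis, and with no related Grade 4 event or related anaphylaxis. Inpatient admission makes this an SAE under 7.4.

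**Step 4. Side check on the neighbouring pause rule.** Section 7.8.4 gives 8:0 as the smallest vaccine-to-placebo split of suspected severe cases for which the 90% lower bound of the relative risk exceeds 1. At 2:1 allocation with equal follow-up per subject, the exact lower limit for the vaccine share with n:0 cases is 0.05^(1/n), and RR = 0.5 × p/(1 − p).

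- 7:0: p = 0.6518, RR lower bound 0.936.
- 8:0: p = 0.6877, RR lower bound 1.101.

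The stated 8:0 is reproduced. The rule counts suspected cases, so it does not wait for the EAC.

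**The case against.** The strongest reply is that the dangerous events are already covered. Section 7.8.4 is triggered by observation, not by adjudication. The severe definition is broad: abnormal respiratory rate, heart rate or oxygen saturation, shock, organ dysfunction, ICU admission or death. AESIs keep their own 24-hour rule, and nothing in 7.11 suspends it. All of this stands, and it rules out three stronger readings.

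- A reader might infer that serious reactions with COVID-like symptoms drop out of the stopping-rule pathway altogether. They do not. Only the related-SAE trigger is affected, and only for the residual class in Step 3.
- A reader might infer that serious cardiac, thromboembolic or respiratory reactions would go unreported. Many of these, including myocarditis and pulmonary embolism, are on the AESI list in Appendix A. The list at hand is that of version 6.0; the version 7.0 appendix is not in the text available, though Section 7.8.1 refers to it.
- A reader might infer that the DSMB would not see these events. Section 12.1 gives it all available unblinded safety data, and nothing confines it to SAE listings.

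It can also be said that 7.11 does not forbid earlier filing. Section 7.9 still has a serious AE recorded as an SAE, and 7.10.2 prefers a known diagnosis to symptoms. An investigator who files early breaks no rule. But a site that waits can also point to the protocol, and 7.11, being the more specific text, is the one it would reasonably follow.

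Finally, routing suspected endpoint events to their own CRF is a legitimate design. It answers where the event is recorded. It does not show that the COVID-19 CRF carries the causality assessment, and it does not resolve the contradiction with 7.9.

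**Conclusion.** The contradiction is in the text and applies to both segments. Its practical reach is narrow: a serious suspected-COVID-19 event that meets no severe-COVID-19 criterion, is not an AESI, and is neither a related Grade 4 AE nor related anaphylaxis. For that event, a site following 7.11 may defer the SAE report, the causality assessment on the SAE form and the related-SAE notification until adjudication.

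The length of the deferral cannot be given. It equals the adjudication time, which the protocol does not state and which the EAC Charter, not available here, may limit. Any figure in days or weeks, or any claim about how many DSMB reviews would be missed, would be an assumption. Nor do the documents say how many subjects would fall in the residual class.

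The conclusion assumes that a site would apply 7.11 in preference to 7.9 where they differ, and that no Charter or site manual already settles the matter. The point deserves correction because it concerns safety reporting and is cheap to fix. It does not threaten the efficacy analysis.

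**What to change.** Reconcile 7.11 with 7.9, 7.4 and 7.8.4 by stating which clock governs a serious, unadjudicated suspected case, in both segments. The wording should ensure that:

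- SAE reporting does not wait for the EAC once the site has grounds to consider the event not COVID-19, for example a negative RT-PCR or an alternative diagnosis;
- 7.11 does not suspend the AESI rule in 7.9;
- an event reported as an SAE moves to the COVID-19 CRF if the EAC later confirms COVID-19;
- the EAC decision continues to govern the efficacy endpoint only.

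This needs about one changed sentence in 7.11, plus the AESI clarification and a memo to sites. The downside is that some SAEs will be filed and later reclassified. Endpoint adjudication and the primary analysis are unchanged.
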